12.1	Appendix A: Grading Laboratory Values according to CTCAE Version 5	20
12.2	APPENDIX B: Noncompartmental Pharmacokinetic Analysis	21
12.2.1	Handling Missing or Non-Quantifiable Data.....	21
12.2.2	Pharmacokinetic Parameter Calculation	21
12.2.2.1	Criteria for the Calculation of Apparent Terminal Elimination Rate Constant and Half-life	21
12.2.2.2	Criteria for Calculation and Reporting of Area Under the Concentration-time Curve ...	22
12.2.3	Treatment of Outliers in Pharmacokinetic Analysis	22

List of abbreviations and definitions of terms

Abbreviation or Term	Definition/Explanation
AE	Adverse event
Ae_{0-24h}	Amount of unchanged drug recovered in urine over 0 - 24 hours post dose
ALT	Alanine aminotransferase
AST	Aspartate transaminase
AUC_{0-24}	The area under the plasma concentration versus time curve from the zero to 24 hours
AUC_{inf}	Area under the curve from time 0 to infinity
AUC_{last}	The area under the plasma concentration versus time curve from the zero to the last quantifiable plasma concentration
C_{max}	Concentration maximum (peak)
CL_R	Renal clearance over a time interval calculated by Ae/AUC at the same time interval (0-24 h in this study).
CL/F	Apparent clearance (CL/F) calculated following extravascular drug administration
CRO	Contract Research Organization
DSC	Data Safety Committee
ECG	Electrocardiogram
eCRF	Electronic Case Report Form
ELF	Enhanced Liver Fibrosis (Score)
EOS	End of Study
fe_{0-24h}	Percentage of the administrated drug recovered in urine over 0 -24 hours postdose
GCP	Good Clinical Practice
GGT	Gamma glutamyl transferase
HSD	Hydroxysteroid dehydrogenase
LISR	Local injection site reactions
MedDRA	Medical Dictionary for Regulatory Activities
MRI	Magnetic resonance imaging
NASH	Non-alcoholic steatohepatitis
NHV	Normal healthy volunteers
PBO	Placebo
PD	Pharmacodynamic
PK	Pharmacokinetic
PT	Preferred Term
QRS	QRS duration (complex) – a structure on the ECG that corresponds to the depolarization of the ventricles
QT	QT interval – a measure of the time between the start of the Q wave and the end of the T wave in the heart's electrical cycle
RNAi	RNA interference
SOC	System Organ Class
$t_{1/2}$	terminal elimination half-life
T_{max}	Time to maximum observed plasma concentration (C_{max})
TEAE	Treatment-emergent adverse event
TESAE	Treatment-emergent serious adverse event

ULN	Upper Limit of Normal
Vz/F	Apparent terminal-phase volume of distribution following extravascular drug administration

1. INTRODUCTION

AROHSD1001 is a first in human dose-ranging study to assess the safety and tolerability of ARO-HSD in healthy volunteers and then in patients with NASH. Treatment with ARO-HSD is expected to reduce hepatic production of the HSD17 β 13 protein via RNAi.

This statistical analysis plan (SAP) is designed in compliance with ICH E9 to outline the methods to be used in the analysis of study data in order to evaluate the study objective(s) from Arrowhead Pharmaceuticals, Inc. (Sponsor) protocol AROHSD1001 Version 7.0, dated 12 March 2021. Populations for analysis, data handling rules, statistical methods, and formats for data presentation are provided. The statistical analyses and summary tabulations described in this SAP will provide the basis for the results sections of the clinical study report (CSR) for this trial.

An approved and signed SAP is required prior to database lock.

The formats for the tables, figures, and listings (TFLs) described in this SAP are provided in a companion document. A table of contents for the TFLs will be included in the companion document.

EMB Statistical Solutions, LLC (EMB) will have responsibility for performing the analyses outlined in this SAP. The Sponsor will have responsibility for performing the PK noncompartmental analysis (NCA) (Appendix B).

2. OBJECTIVES, ENDPOINTS AND HYPOTHESES

2.1 Objectives and Endpoints/Estimands

Primary Endpoint

The incidence and frequency of adverse events (AEs) possibly or probably related to treatment after single doses in healthy volunteers and after multiple doses in patients with NASH or suspected NASH.
Secondary Endpoints

Pharmacokinetics of ARO-HSD
Exploratory Endpoints
(All Cohorts) 
Change in fasting LDL-C, Total Cholesterol, non-HDL-C, HDL-C, VLDL-C, and triglycerides compared to baseline
(Patient cohorts 1b, 3b and 4b) 
Change in ALT and in AST as a marker of ARO-HSD activity compared to baselineChange in cytokeratin-18 compared to baselineChange in IL-1β, IL-6, IL-10, INF-gamma, and TNF-α compared to baselineChange in retinol and retinol binding protein compared to baselineChange in liver fat using MRI-PDFF compared to baselineChange in blood exosomal HSD17β13 mRNA levels (if feasible) compared to baselineChange in blood exosomal PNPLA3 mRNA levels (if feasible) compared to baselineChange in Enhanced Liver Fibrosis (ELF) Score at EOS compared to baseline

- Change in Pro-C3 at EOS compared to baseline
- Liver biopsy derived HSD17 β 13 mRNA expression compared to baseline
- Liver biopsy derived HSD17 β 13 protein expression compared to baseline in response to multiple doses of ARO-HSD (if scientifically feasible)
- Liver biopsy derived change in PNPLA3 mRNA expression compared to baseline
- Liver biopsy derived change in PNPLA3 protein expression compared to baseline in response to multiple doses of ARO-HSD (if scientifically feasible)

2.2 Hypotheses and/or Estimations

No formal statistical hypotheses will be tested in this study. Any reported statistical tests will be considered exploratory.

3. STUDY OVERVIEW

3.1 Study Design

The study will be conducted in approximately 50 adult males and females, aged 18 through 65 years (minimum of 19 years of age for NASH or suspected NASH patients) with BMI between 18.0 and 40.0 kg/m² enrolled and dosed as described in the table below. Cohorts 1, 2, 3, and 4 (NHVs) are double-blind, randomized with a 1:1 (active:PBO) ratio to reduce bias. Cohorts 1b, 3b and 4b are open-label with all subjects receiving active treatment and include patients with NASH or suspected NASH.

Cohort Summary

Cohort	Population	Blinding	# Subjects	Dosing Schedule
1	NHVs	Double blind	8 (4 active: 4 PBO)	25 mg Day 1 only
1b	Patients with suspected NASH (biopsies on screen and Day 71)	Open-Label	up to 6 (all active)	25 mg Days 1, 29
2	NHVs	Double blind	8 (4 active: 4 PBO)	50 mg Day 1 only
3	NHVs	Double blind	8 (4 active: 4 PBO)	\leq 100 mg Day 1 only
4	NHVs	Double blind	8 (4 active: 4 PBO)	\leq 200 mg Day 1 only
3b	Patients with suspected NASH (biopsies on screen and Day 71)	Open-Label	up to 6 (all active)	\leq 100 mg Days 1, 29
4b	Patients with suspected NASH (biopsies on screen and Day 71)	Open-Label	up to 6 (all active)	\leq 200 mg Days 1, 29

For NHV subjects in Cohorts 1 through 4, the duration of the study clinic visits is approximately 158 days from screening to the End-of-Study (EOS) visit. For subjects in Cohorts 1b, 3b and 4b, the duration of the study clinic visits is approximately up to 173 days from screening to the EOS visit.

The final analysis will be completed following database lock after the last subject's last visit. Individual cohorts may be summarized prior to database release; however, the final analysis will be based on all available data collected in the study.

3.2 Sample Size

This study represents a proof of principle study, and as such no formal sample size calculation was performed.

Approximately 50 subjects may be enrolled in the study (not including replacements or optional expansion cohort).

4. COVARIATES AND SUBGROUPS

4.1 Planned Covariates

There are no predetermined covariates.

4.2 Subgroups

There are no planned subgroup analyses.

5. DEFINITIONS

Day 1:

For each subject, Day 1 is defined as the first day that protocol-specified study treatment is administered to the subject.

End of Study (EOS) Date:

For each subject, the EOS date is the study completion/early termination date recorded on the eCRF.

Study Day:

For each subject, and for a given date of interest, study day is defined as the number of days relative to Day 1:

- After first dose date: study day = date of interest – Day 1 date + 1
- Prior to first dose date: study day = date of interest – Day 1 date, so that the day prior to Day 1 is Day -1

Study End Date:

The study end date is when the last subject finishes the EOS visit.

Baseline Values:

For all variables, baseline is defined as the last non-missing value obtained prior to the first dose administration on Day 1.

For ECG, if a triplicate is taken prior to the first dose administered on Day 1, baseline is defined as the mean over the set of triplicate assessments.

Analysis Day:

Selected endpoints will be summarized based on Analysis Day defined using Study Day as below.

Scheduled Visit/ Analysis Day	Day 8	Day 15	Day 29	Day 43	Day 57	Day 71	Day 85	Day 99	Day 113
Study Day Window Cohort 1-4	[6,10]	[13,17]	[27,31]	[41, 45]	[55,59]	[69,73]	[83,87]	[97,101]	[111,115]
Study Day Window Cohort 1b,3b,4b	NA	[13,17]	[27,31]	NA	[55,59]	[66,76]	[83,87]	NA	[108,118]

If there is more than one record in a study day window, the analytical record for that specific analysis day will be defined as the record closest to the scheduled visit day. If two records are equidistant from the scheduled visit day, then the earlier record will be chosen. If there are multiple records on the same day, the last record will be used.

Duration of study:

EOS date – Day 1 date + 1

Treatment-Emergent Adverse Event (TEAE):

TEAEs are defined as adverse events occurring on or after the first dose of study treatment through EOS or pre-treatment existing conditions that worsen after the investigational product administration.

Treatment-emergent SAEs (TESAEs):

TESAEs are defined as serious adverse events occurring on or after the first dose of study treatment through EOS or pre-treatment existing conditions that worsen after the investigational product administration.

TEAE at Injection Site:

TEAE occur at the injection site. MedDRA Preferred Terms which are included in LISR are listed in Protocol Section 16.2.

TEAE Related to Local Injection Site Reaction (LISR):

This is defined as adverse events at the injection site which start on the day after the injection of the investigational product and persist for at least 48 hours. MedDRA Preferred Terms which are included in LISR are listed in Protocol Section 16.2.

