#### 11. ADVERSE EVENTS

The PI and clinical facility staff are responsible for detection, recording and reporting of events that meet the criteria and definition of various AEs as listed below. Adverse events will be recorded from time of signed consent through to EOS; only AEs that occur post-dose will be considered treatment-emergent. The PI and clinical facility staff are responsible for detection, recording and reporting of pregnancy and appropriate follow up. Information regarding any reported pregnancy should be collected for at least 1 year after birth or longer if it is decided that addition follow-up is required or until the end of the pregnancy.

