#### 11.1 **Definitions**

An **Adverse Event (AE)** is any untoward medical occurrence in a patient or clinical investigation patient administered a pharmaceutical product and which does not necessarily have to have a causal relationship with this treatment. An AE can therefore be any unfavorable and unintended sign (including an abnormal laboratory finding or diagnostic test), symptom, or disease temporally associated with the use of a medicinal (investigational/experimental) product,

whether related to this product or not. (Refer to ICH E2a: Clinical Safety Data Management: Definitions and Standards for Expedited Reporting, 27 October 1994).

Treatment-emergent AEs will be defined as AEs with onset after administration of the study drug, or when a pre-existing medical condition increases in severity or frequency after study drug administration.

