# 11.3 Timing, Frequency, and Method of Detecting AEs

Any pre-existing conditions or signs and/or symptoms present in a participant prior to the start of the study (i.e., before informed consent) should be recorded as Medical/Surgical History.

All AEs occurring after informed consent and on or before the final visit must be reported as AEs; only AEs that occur post-dose will be considered treatment-emergent. All AEs must be recorded irrespective of whether they are considered drug-related. AEs will be collected through the EOS or through 30 days after the last dose whichever is longer.

At each visit/assessment in the period defined above, AEs will be evaluated by the PI (or medically qualified designee) and recorded.

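### The SAP ends treatment emergence at early termination, short of protocol 11.3's 30-day post-dose AE collection, so some related events in early leavers could be left out of the primary endpoint tables

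*SAP*

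**What the plan says.** **SAP.** Section 5 states that "TEAEs are defined as adverse events occurring on or after the first dose of study treatment through EOS", with a second limb for "pre-treatment existing conditions that worsen after the investigational product administration". The first limb has an end date and the second has none. TESAEs are defined the same way. Section 5 also states: "For each subject, the EOS date is the study completion/early termination date recorded on the eCRF". Section 9.6.1 reports related events as treatment-related TEAEs and TESAEs, and adds a by-subject AE listing that carries a TEAE flag. Section 10 declares no change from the protocol-defined analyses.

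**Protocol.** On treatment emergence, section 11.1 sets a start and no end: "Treatment-emergent AEs will be defined as AEs with onset after administration of the study drug". On collection, the protocol speaks with more than one voice:
- Section 11.3: "AEs will be collected through the EOS or through 30 days after the last dose whichever is longer".
- Section 11.3, earlier in the same paragraph: "All AEs occurring after informed consent and on or before the final visit must be reported as AEs".
- Section 11, opening: "Adverse events will be recorded from time of signed consent through to EOS".
- Schedule of Assessments, Tables 1 and 2: the AE row ends at the EOS/early termination column.

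The primary endpoint in both documents is the incidence and frequency of AEs possibly or probably related to treatment.

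**The concern.** The 30-day sentence in protocol 11.3 extends collection only for someone who leaves soon after a dose. For that same person, the SAP closes the treatment-emergent window on the day of leaving. A new related event in between would fall within the 11.3 collection period and be treatment-emergent under 11.1, yet fail the SAP definition. It would then be absent from every table that reports the primary endpoint, while the participant stays in the Safety Analysis Set denominator. The omission can only lower a group's count. The groups are small enough for one participant to be visible, and SAP section 10 does not disclose the narrowing.

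**Working it through.** **Step 1: fix the EOS day.** Screening opens at Day -45 for volunteers (Table 1) and Day -60 for patients (Table 2). EOS is Day 113 (SAP section 5 analysis-day table; Table 2). Then 45 + 113 = 158 and 60 + 113 = 173, which reproduces both durations in protocol 7.5.

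**Step 2: completers.** The 30-day period ends on (day of last dose + 30). The earliest in-window EOS comes from the SAP section 5 windows.

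| Group | Last dose | 30 days ends | Earliest EOS | Margin |
|---|---|---|---|---|
| Volunteers | Day 1 | Day 31 | Day 111 | 80 days |
| Patients | Day 29 | Day 59 | Day 108 | 49 days |
| Patients, second dose at latest in-window day | Day 31 | Day 61 | Day 108 | 47 days |

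For completers EOS is always the later date, so the two windows agree.

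**Step 3: early leavers.** Gap = max(0, day of last dose + 30 - day of early termination).

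| Last dose | Early termination | Gap |
|---|---|---|
| Day 1 | Day 3 | 28 days |
| Day 1 | Day 8 | 23 days |
| Day 1 | Day 15 | 16 days |
| Day 1 | Day 29 | 2 days |
| Day 29 | Day 29 | 30 days |
| Day 29 | Day 43 | 16 days |
| Day 29 | Day 57 | 2 days |
| Day 29 | Day 59 or later | 0 days |

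The maximum is 30 days, when termination falls on the day of dosing. Anyone leaving 30 or more days after the last dose has no gap.

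**Step 4: which events are at risk.** An event is lost from the tables only if all of these hold:
- it is collected, as the 30-day sentence of 11.3 requires;
- it is of new onset, because the worsening limb of the definition has no end date;
- it starts after the early termination date and within 30 days of the last dose.

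To change participant-level related incidence, it must also be judged related, in someone with no earlier related TEAE.

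**Step 5: weight of one such participant.** 1/4 = 25 points in an active volunteer group; 1/6 = 16.7 points in a patient cohort of 6; 1/16 = 6.25 points in pooled placebo (4 cohorts x 4).

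**Step 6: how often.** Neither document gives a dropout or AE rate. As an illustration with assumed inputs only, let e be the proportion of active participants leaving within 30 days of the last dose, and q the proportion of those with a new related event in the gap and no earlier one. Planned active participants number 16 + 18 = 34. With independent participants, the chance of missing at least one is 1 - (1 - eq)^34.
- e = 2%, q = 5%: 1 - 0.999^34 = 3%.
- e = 10%, q = 20%: 1 - 0.98^34 = 50%.

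The range is too wide to serve as an estimate.

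**The case against.** **The events may never be collected.** Only one sentence requires collection beyond EOS. The opening of section 11, the other sentence of 11.3 and the AE row of the Schedule all stop at EOS, the final visit or early termination. The one later contact, the 90-day call, covers contraception and pregnancy. If those passages govern, the SAP window matches collection. This stands, and it makes the point conditional. It does not remove it: 11.9 defines post-study events by reference to the period in 11.3, 11.1 sets no upper limit, and the SAP should not depend on an unresolved conflict in the protocol.

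**The EOS field is not fully specified.** "the EOS date is the study completion/early termination date recorded on the eCRF" does not say whether, for someone still under AE follow-up, the date entered is the last visit or the close of follow-up. If it is the latter, there is no gap. This also stands as an uncertainty.

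**Stronger readings the documents do not support.**
- A reader might infer that collected events are certainly being dropped. The documents do not show that any post-termination event reaches the database.
- A reader might infer that people who leave because of an AE are lost from the endpoint. The new-onset event that led to withdrawal began before termination, so it is already a TEAE. If it was related, that participant is already counted, and a later event could add only a further term or event count.
- A reader might take a case such as leaving 7 days after a dose, with (30 - 7)/30 = 77% of the period cut off, as the size of the loss. That is a share of days at a chosen date, not a share of events.

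**The listing keeps the event visible.** A collected event should appear in the by-subject listing, and a serious one in the SAE listing. That limits the harm but does not correct an incidence table.

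**Conclusion.** The SAP definition is wrong as written: its window is narrower than the collection period in protocol 11.3 and the open-ended definition in 11.1, and section 10 does not say so. The consequence is conditional on AEs being collected as 11.3 requires and on the recorded EOS date being the date of leaving. Given both, a new-onset related event after early termination but within 30 days of the last dose is left out of the TEAE, TESAE and treatment-related tables.

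Completers, later leavers, events that began before withdrawal and worsening pre-existing conditions are unaffected. The possible shift is 25 or 17 points for a single participant in the smallest groups; its probability cannot be derived from the documents. This is a descriptive study with no hypothesis tests, so the issue is the completeness of the reported incidence. It should be corrected because it reaches the primary endpoint and the correction costs little.

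**What to change.** 1. **SAP section 5.** Define TEAE and TESAE as onset on or after first dose through the later of EOS/early termination and 30 days after the last dose, keeping the limb on worsening conditions. Dropping the upper limit, to match protocol 11.1, would also work.
2. **Protocol.** Reconcile the collection period across the opening of section 11, both sentences of 11.3 and the AE row of Tables 1 and 2.
3. **If the EOS cut-off is kept**, declare it in SAP section 10 as a departure from the protocol.

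The cost is one line in the SAP for the two definitions and short wording changes in the protocol. Results for completers do not change. The small downside is that early leavers may need AE follow-up to day 30 after the last dose, for which the Schedule shows no contact, although 11.3 already requires it.

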# 11.5.2 AEs at the Injection Site and Local Injection Site Reactions (LISRs)

AEs at the injection site will be graded as either Mild, Moderate or Severe. A local injection site reaction is defined as an adverse reaction (usually immunologic) developing at the site of injection and lasting at least 48 hours. For the data reporting and analysis purposes, the definition of LISR based on duration of at least 48 hours and based on the specified MedDRA preferred times is provided in Appendix 16.2. Photographs of local reactions around injection site should be obtained at the time of reporting and at the approximate time of resolution.

- Mild: Tenderness with or without associated symptoms (e.g., warmth, erythema, itching), mild pain or mild edema
- Moderate: Pain with associated phlebitis or lipodystrophy
- Severe: Tissue ulceration or necrosis with associated severe tissue damage or if operative intervention is indicated

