# 16.2 Local Injection Site Reactions (LISRs)

The following MedDRA Preferred Terms determined by the Sponsor's pharmacovigilance personnel represent the local injection site reaction:

Injection site discomfort	Injection site abscess
Injection site discoloration	Injection site abscess sterile

Injection site erythema	Injection site atrophy
Injection site irritation	Injection site calcification
Injection site inflammation	Injection site cellulitis
Injection site induration	Injection site dermatitis
Injection site pain	Injection site erosion
Injection site oedema	Injection site fibrosis
Injection site pruritus	Injection site indentation
Injection site rash	Injection site necrosis
Injection site urticaria	Injection site nodule
Injection site reaction	Injection site ulcer
Injection site swelling	

LISRs will only include events that start on the day of injection and persist for at least 48 hours post injection (i.e., event onset date on the day of injection and resolution date not on the day of injection or the day after the injection) will be included. Events with onset date on the day of injection and missing resolution date will also be included in the summary.

The following calculation will be utilized to determine the percentage of injections leading to local injection site reactions:

 $(A/B)^*$ , where A = number of injections with a local injection site reactions, and B = total number of injections.

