9.6.1 Adverse Events

Adverse event (AEs) will be coded using the Medical Dictionary for Regulatory Activities (MedDRA, the latest available version) and data will be summarized by System Organ Class (SOC) and a Preferred Term.

A table providing an overall summary of AEs will be produced which will include the number of TEAEs; the number and percentage of participants reporting at least one: TEAE, TESAE, grade 3 (severe) or higher TEAE, TEAE related to study treatment (possibly or probably related to ARO-HSD), TESAE related to study treatment, grade 3 or higher TEAE related to the investigational product and TEAE leading to drug or study withdrawal.

Descriptive statistics summaries of subject incidence will be summarized for all TEAEs, treatment-related TEAEs, TESAEs, treatment-related TESAEs, and TEAEs resulting in investigational product withdrawal or study discontinuation, treatment emergent fatal AEs, TEAE at injection site and TEAE related to LISR will be tabulated by SOC in alphabetical order and PT in descending order of frequency. Descriptive summaries will include count and percent of subjects as well as number of events..

Descriptive statistics summaries of subject incidence of TEAEs, TEAE at injection site and TEAE related to LISR by SOC, PT, and severity will be provided. Subjects will be counted once under the highest severity reported within each SOC and PT. The events will be counted the number of times they occur within each SOC and PT.

Descriptive statistics summaries of subject incidence of TEAEs by SOC, PT, and relationship to investigational product will be provided. Subjects will be counted once under the closest relationship reported within each SOC and PT. Events will be counted the number of times they occur within each SOC and PT.

A by-subject AE data listing, including verbatim term, MedDRA SOC and PT, TEAE flag, seriousness, severity, outcome and relationship to study treatment will be provided. Separate listings will be generated for SAEs.

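### The SAP counts local injection site reactions from the day after injection, while Protocol 16.2 counts only those starting on the day itself, so the LISR tables would hold none of the 16.2-defined reactions

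*SAP*

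**What the plan says.** Protocol 11.5.2 first gives a general description of an LISR: an adverse reaction at the injection site that lasts at least 48 hours, with no limit on the day of onset. It then points to Appendix 16.2 for the working definition: "For the data reporting and analysis purposes, the definition of LISR based on duration of at least 48 hours", together with the listed preferred terms.

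Protocol Appendix 16.2 restricts onset: "LISRs will only include events that start on the day of injection and persist for at least 48 hours post injection". It restates this in terms of dates: "event onset date on the day of injection and resolution date not on the day of injection or the day after the injection". It also settles incomplete records: "Events with onset date on the day of injection and missing resolution date will also be included in the summary". Finally, it defines a percentage A/B, where A is the number of injections with an LISR and B is the total number of injections.

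SAP section 5 limits the corresponding analysis term to injection-site events that meet this condition: "which start on the day after the injection of the investigational product and persist for at least 48 hours". It cites Protocol 16.2 only for the list of preferred terms. It gives no rule for a missing resolution date.

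SAP 9.6.1 plans two summaries that use this definition: "TEAE at injection site and TEAE related to LISR will be tabulated by SOC" and preferred term, and "TEAE at injection site and TEAE related to LISR by SOC, PT, and severity will be provided". SAP section 10 states that the planned analyses do not differ from those in the protocol.

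**The concern.** The two onset rules exclude each other. If the SAP sentence is programmed literally, an event that starts on the day of injection and persists is left out of the LISR tables, although Appendix 16.2 counts it. An event that starts the next day is counted, although the appendix excludes it. The tables could show no LISRs in a group that had some.

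Quality control would not necessarily catch this. SAP 8.7 relies on independent programming, and two programmers working from the same sentence would agree with each other.

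LISR is not a listed endpoint. It does matter to the study's single objective, safety and tolerability: injection site reactions are a named risk in Protocol 5.7, and LISRs are a listed safety assessment in Protocol 10.7.

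**Working it through.** The plan states no figure on this point, so there is none to reproduce. The check compares the two rules on every possible pair of onset and resolution days.

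**Rules.** Let *d* be the study day of an injection, *o* the onset day and *r* the resolution day.
- Protocol 16.2: *o* = *d*, and *r* is neither *d* nor *d* + 1, or is missing.
- SAP section 5: *o* = *d* + 1, with a duration of at least 48 hours. On calendar dates this is read as *r* − *o* ≥ 2. Records with missing *r* are kept, which is an assumption in the SAP's favour because the SAP is silent.

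**Onset overlap.**
- Healthy volunteers have one injection, on Day 1. The protocol onset day is {1} and the SAP onset day is {2}, so nothing is shared.
- Patients have injections on Day 1 and on Day 29 ± 2 (Protocol Table 2). With the second injection on day *s* = 27 to 31, the protocol onset days are {1, *s*} and the SAP onset days are {2, *s* + 1}. These sets do not intersect for any *s*.

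**Count of onset/resolution patterns, follow-up to Day 113, second injection on Day 29.**

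| Group | Protocol 16.2 | SAP section 5 | Both |
|---|---|---|---|
| Healthy volunteers | 111 + 1 missing = 112 | 110 + 1 missing = 111 | 0 |
| Patients | 112 + (83 + 1) = 196 | 111 + (82 + 1) = 194 | 0 |

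These are possible date patterns, not expected events. If the SAP onset is changed to the day of injection and missing resolution dates are kept, the two definitions select the same patterns: 112 of 112 and 196 of 196.

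**Base of injections** (Protocol Table 4; one injection per dose, Protocol 10.5).
- Healthy volunteers, active: 4 cohorts × 4 = 16.
- Healthy volunteers, placebo: 4 cohorts × 4 = 16.
- Patients: up to 3 cohorts × 6 × 2 doses = 36.
- Total: 16 + 16 + 36 = 68.
- The Protocol Synopsis allows two extra patients in each of Cohorts 1b and 3b. If all are dosed twice, this adds 2 × 2 × 2 = 8, giving 76.
- Replacements and the optional expansion cohort are not included.

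**Duration test.** Suppose the onset days agreed. The date rule in 16.2 and a strict 48-hour test from onset could still differ. An event starting at 23:59 on the injection day and resolving at 00:00 two calendar days after injection lasts 24 h 1 min and passes the date rule. One starting at 00:01 and resolving at the same 00:00 lasts 47 h 59 min and also passes. Disagreement is confined to durations between these limits, and every event of 48 hours or more passes the date rule.

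**The case against.** The strongest reply is that the SAP wording is a slip, either for the day of injection or for onset on that day but after the injection. Protocol 11.5.2 and SAP section 10 both point towards Appendix 16.2. That may be right, but the sentence as written specifies the next day and nothing in the SAP corrects it. Even on the charitable reading, the rule for missing resolution dates is absent.

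A second reply is that the general description in 11.5.2 has no onset-day limit, so a next-day reaction can be an LISR in that sense. This is true, and it is why the conclusion is confined to LISRs as Appendix 16.2 defines them. For analysis, 11.5.2 itself defers to that appendix.

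A third is that the duration contrast is weak. The SAP's 48 hours echoes the protocol's own phrase, and most of the 24-to-48-hour disagreement arises because the date rule in 16.2 only approximates 48 hours. Neither document says that adverse event times are recorded to the minute. This stands: the duration difference is minor and the finding does not depend on it.

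A fourth is that little is lost. The SAP has a separate category for any "TEAE occur at the injection site", tabulated in the same two ways, and the events also appear in the all-event tables and the listing. This stands too, and it limits the consequence. None of those outputs applies the LISR definition, however, so none gives the LISR incidence that the protocol specifies.

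Finally, table formats are in a companion document not available here, so the A/B percentage may be planned there. It is a secondary point.

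**Conclusion.** The concern holds and should be fixed. The SAP and Protocol 16.2 set incompatible onset days, the difference is undeclared, and the overlap between them is zero for every injection. Both LISR tables are affected if programmed as written. LISR incidence would be wrong in any active group, or in the pooled placebo group, that has persistent reactions starting on the day of injection or the day after. A group with neither kind of event is unaffected.

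The base is 68 planned injections, or 76 with the extra patients. The documents give no LISR rate, so no number of misclassified events is claimed. The primary endpoint and the other adverse event tables are not touched. The conclusion rests on the literal SAP wording and on Appendix 16.2 being the analysis definition, as Protocol 11.5.2 states.

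**What to change.** Before database lock, replace the onset and duration wording in SAP section 5 with the single date rule of Protocol 16.2:
- a listed preferred term;
- an onset date equal to the actual date of an injection;
- a resolution date that is neither that day nor the next, or is missing.

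Add the A/B percentage from Protocol 16.2 to SAP 9.6.1. If next-day onset was intended, state and justify the departure in SAP section 10 instead.

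The cost is small: short edits to sections 5 and 9.6.1, one derivation flag and one summary row. Adverse event dates and injection dates are already collected. SAP 9.6.8 already summarises subjects by number of injections received, so B is obtained by summing over subjects.
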